9.4. Ethical conduct of the study

The study will be conducted in accordance with legal and regulatory requirements, as well as with scientific purpose, value and rigor and follow generally accepted research practices described in in Guidelines for Good Pharmacoepidemiology Practices (GPP) issued by the International Society for Pharmacoepidemiology (ISPE), Good Practices for Outcomes Research issued by the International Society for Pharmacoeconomics and Outcomes Research (ISPOR), and the Good Research for Comparative Effectiveness (GRACE) Principles. 18-20

10. MANAGEMENT AND REPORTING OF ADVERSE EVENTS/ADVERSE REACTIONS

This study involves electronic health records data that exist as structured data by the time of study start or a combination of existing structured data and unstructured data, which will be converted to structured form during the implementation of the protocol solely by a computer using automated/algorithmic methods, such as natural language processing.

In these data sources, individual patient data are not retrieved or validated, and it is not possible to link (i.e., identify a potential association between) a particular product and medical event for any individual. Thus, the minimum criteria for reporting an adverse event (AE) (i.e., identifiable patient, identifiable reporter, a suspect product, and event) cannot be met.

11. PLANS FOR DISSEMINATING AND COMMUNICATING STUDY RESULTS

In the event of any prohibition or restriction imposed (e.g., clinical hold) by an applicable competent authority in any area of the world, or if the investigator, Analysis Group, is aware of any new information which might influence the evaluation of the benefits and risks of a Pfizer product, Pfizer should be informed immediately.

Based on the analysis results and discussions with Pfizer, an abstract and/or manuscript may be prepared. If feasible, an abstract will be submitted to the Society for Melanoma Research (SMR) 2023 conference. A study report summarizing the background, objectives, methods, results, and conclusion of the study will be prepared.

13. LIST OF TABLES

Table	Description
Table 1. Key exposures, outcomes, and patient	Table summarizing exposure, outcome, and
baseline characteristics in the treatment groups	patient baseline characteristics that will be
	evaluated within the study.
Table 2. Kaplan-Meier analyses comparing OS	Table summarizing KM analyses from the
between treatment groups	ENCO+BINI, DAB+TRAM and VEM+COBI
	treatment groups
Table 3. Unadjusted and adjusted hazard ratios	Table summarizing hazard ratios comparing
comparing OS between treatment groups	ENCO+BINI to the DAB+TRAM and
	VEM+COBI treatment groups

14. LIST OF FIGURES

None.

ANNEX 1. LIST OF STAND-ALONE DOCUMENTS

None.

ANNEX 2. ADDITIONAL INFORMATION

Not applicable.

APPENDIX: TABLE SHELLS

Appendix Table 1: Baseline patient characteristics, by treatment group

	ENCO+BINI	VEM+COBI	DAB+TRAM
	N =	N =	N =
Demographic Characteristics			
Age at baseline (years)			
Mean (SD)			
Median (IQR)			
Sex, n (%)			
Female			
Male			
Missing, n (%)			
Race, n (%)			
White/Caucasian			
Black/African American			
Asian			
Native American or Pacific Islander			
Other			
Missing			
BMI (kg/m²)			
Mean (SD)			
Median (IQR)			
Missing, n (%)			
Year of treatment initiation, n (%)			
2014			
2015			
2016			
2017			
2018			
2019			
2020			
2021			
Region, n (%)			
North America			
Europe			
Australia			
Other			
Missing			
Disease-Related Characteristics			
Number of organs involved (metastatic sites	s) at baseline, n (%)		
1			
2			
≥3			
Missing			
Lung metastasis, n (%)			
No			
Yes			

Missing				
Liver metastasis, n (%)				
No				
Yes				
Missing				
Other metastasis, n (%)				
No				
Yes				
Missing				
Time from initial melanoma diagnosis to	metastatic disease (months)		
Mean (SD)				
Median (IQR)				
Missing, n (%)				
Time from metastatic melanoma diagnos	sis to treatment initiation (m	onths)		
Mean (SD)				
Median (IQR)				
Missing, n (%)				
BRAF mutation status, n (%)				
V600E				
V600K				
ECOG performance status, n (%)				
0				
1				
≥2				
Missing				
AJCC stage at initial melanoma diagnosis,	n (%)			
0				
I				
П				
III				
IV				
Unknown				
Missing				
AJCC stage at treatment initiation, n (%)				
Stage IIIC				
Stage IV				
Missing				
LDH categories, n (%)				
≤ULN				
> ULN				
Missing				
Treatment-Related Characteristics				
Treatment experience in the therapeutic s	setting, n (%)			
Treatment naive				
Prior 1L IO therapy				
Prior systemic therapies in the adjuvant setting, n (%)				
Yes				

N-				
No				
Prior IO or chemotherapy in the adjuvan	Prior IO or chemotherapy in the adjuvant setting, n (%)			
Yes				
No				
Prior surgery in the adjuvant setting, n (Prior surgery in the adjuvant setting, n (%)			
Yes				
No				
Number of LOTs after targeted therapy, n (%)				
0				
1				
≥2				
Missing				

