There is increasing interest in evaluating comparative effectiveness of BRAF-/MEK-inhibitor therapies. In a recent study, we showed that overall survival (OS) for metastatic BRAFV600-mutant melanoma patients was similar across the COLUMBUS trial and real-world practice data from the Flatiron Health database (Hazard Ratio [HR] = 0.94, 95% Confidence Interval [CI]: 0.43, 1.45) after harmonizing key patient selection criteria, adjusting for differences in baseline characteristics, and imputing missing data on baseline characteristics. Given this empirical consistency in OS outcomes, pooling patients across these settings can be justified and allows for a larger sample size for assessment of comparative effectiveness of encorafenib + binimetinib versus other targeted therapies. To that end, this study will expand on this prior work and compare OS between patients receiving encorafenib + binimetinib in the pooled Phase 3 COLUMBUS trial and the Flatiron Health Electronic Health Records (EHR) database versus patients receiving other targeted therapies. Baseline profiles of patients will also be compared to characterize differences in patients receiving different therapies and adjustments will be made for

differences across treatment groups in baseline factors associated with OS. Missingness for key baseline characteristics will be addressed using a validated multiple imputation approach.¹²

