Body mass index (BMI) at index	Baseline Characteristic / Potential Confounder	COLUMBUS trial data; Flatiron EHR	Defined as weight (in kg) divided by squared height (in m²)
ECOG at index	Baseline Characteristic / Potential Confounder	COLUMBUS trial data; Flatiron EHR	0, 1, Unknown/Missing; defined during the baseline period of both the COLUMBUS trial data and Flatiron EHR
BRAF mutation status	Baseline Characteristic / Potential Confounder	COLUMBUS trial data; Flatiron EHR	V600E, V600K, Unknown/Missing
AJCC disease stage at initial melanoma diagnosis	Baseline Characteristic / Potential Confounder	COLUMBUS trial data; Flatiron EHR	0, I, II, III, IV, or Unknown/Missing; defined at initial melanoma diagnosis for COLUMBUS trial data and Flatiron EHR
AJCC disease stage at treatment initiation	Baseline Characteristic	COLUMBUS trial data	IIIB, IIIC, IVM1a, IVM1b, or IVM1c; defined at treatment initiation in the COLUMBUS trial data. Not available in the Flatiron EHR
Lactate dehydrogenase (LDH) at index	Baseline Characteristic / Potential Confounder	COLUMBUS trial data; Flatiron EHR	Evaluated in units per liter (U/L) and defined at trial baseline in COLUMBUS trial and during the baseline period in Flatiron EHR
Time from initial melanoma diagnosis to metastatic disease	Baseline Characteristic / Potential Confounder	COLUMBUS trial data; Flatiron EHR	Duration (in months) from melanoma diagnosis to the development of metastatic disease
Time from metastatic melanoma diagnosis to treatment initiation	Baseline Characteristic / Potential Confounder	COLUMBUS trial data; Flatiron EHR	Duration (in months) from metastatic melanoma diagnosis to the initiation of treatment
Year of treatment initiation	Baseline Characteristic	COLUMBUS trial data; Flatiron EHR	Calendar year when treatment was initiated
Region	Baseline Characteristic	COLUMBUS trial data; Flatiron EHR	Europe, North America, Australia, Other, or Missing
Treatment experience in the therapeutic setting	Baseline Characteristic / Potential Confounder	COLUMBUS trial data; Flatiron EHR	Indicates whether patients received targeted therapy as first-line treatment (e.g., Treatment naïve) or as second- line treatment after a prior line of immunotherapy treatment (e.g., Prior 1L IO therapy)

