Prior systemic therapies in the adjuvant setting	Baseline Characteristic /Potential Confounder	COLUMBUS trial data; Flatiron EHR	Indicates whether patients previously received systemic therapy (e.g., prior surgery, radiotherapy, immunotherapy, or chemotherapy) before initiating treatment
Prior surgery in the adjuvant setting	Baseline Characteristic / Potential Confounder	COLUMBUS trial data; Flatiron EHR	Indicates whether patients previously used surgery to reduce/remove tumors as a form of treatment
Prior radiotherapy in the adjuvant setting	Baseline Characteristic / Potential Confounder	COLUMBUS trial data; Flatiron EHR	Indicates whether patients underwent radiotherapy among those receiving prior systemic therapy

Prior IO or chemotherapy in the adjuvant setting	Baseline Characteristic / Potential Confounder	COLUMBUS trial data; Flatiron EHR	Indicates whether patients underwent chemotherapy or immunotherapy among those receiving prior systemic therapy
Number of LOTs after TT treatment initiation	Baseline Characteristic / Potential Confounder	COLUMBUS trial data; Flatiron EHR	Indicates the number of LOTs occurring after treatment initiation $(0, 1, \ge 2$, or Missing)
Number of organs involved	Baseline Characteristic	COLUMBUS trial data; Flatiron EHR	Indicates number of organs involved or sites of metastases at baseline (1, 2, or ≥3), with all patients having at least 1 site given diagnosis of metastatic disease. This data was collected and reported in COLUMBUS. In Flatiron EHR, it will be derived based on counting the number of distinct sites recorded as having metastases based on ICD codes.
Presence of lung metastases	Baseline Characteristic	COLUMBUS trial data; Flatiron EHR	Indicates whether patients had lung metastases. This data was collected and reported in COLUMBUS. In Flatiron EHR, it will be derived based on having ICD codes reflecting presence of lung or respiratory organ metastases (ICD-9: 197, 197.1; ICD-10: C78.01, C78.02, C78.1, C78.2, C78.30, C78.39).
Presence of liver metastases	Baseline Characteristic	COLUMBUS trial data; Flatiron EHR	Indicates whether patients had liver metastases. This data was collected and reported in COLUMBUS. In Flatiron EHR, it will be derived based on having ICD codes reflecting presence of liver metastases (ICD-9: 197.7; ICD-10: C78.7)

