8.9. Strengths and limitations of the research methods

The strengths of this study include:

- Key inclusion criteria with respect to diagnosis, disease stage, age, BRAFV600 mutation and ECOG status in the COLUMBUS trial will be applied to the Flatiron RWD to the extent possible to obtain a comparable group of patients across both settings
- Adjustment will be made for multiple baseline characteristics to mitigate bias due to potential differences in these characteristics across the treatment groups
- Concerns about differences in outcome assessment across trial and RWD settings are
 mitigated for OS given the availability of a real-world mortality endpoint in the Flatiron
 RWD that has high sensitivity, specificity, positive predictive values, negative predictive
 values and agreement when compared against the National Death Index (NDI), the goldstandard source for mortality data in the US.¹⁷

The limitations of this study include the following:

- Application of the COLUMBUS trial inclusion criterion requiring at least 1 measurable lesion based on Response Evaluation Criteria in Solid Tumors (RECIST) version 1.1 criteria will not be implemented due to absence in Flatiron EHR of systematic radiographic imaging to assess tumor response as required by RECIST.
- While adjustment will be made for available baseline characteristics across treatment
 groups, differences due to factors that were not adjusted for may still contribute to
 observed differences in OS between settings. For instance, data on number and sites of
 metastases, while systematically collected in the COLUMBUS trial, can only be derived
 based on ICD codes in Flatiron EHR. Based on clinical input, data on number and sites
 of metastases will very likely be underestimated in the Flatiron EHR, and not
 comparable to the corresponding data from COLUMBUS, precluding adjustment for
 these variables.

- The analysis conducted here is analogous to an 'intent-to-treat' perspective, and therefore will not account for potential differences in adherence and post-baseline treatments between trial and real-world settings.
- The COLUMBUS trial was a multi-national trial that recruited patients from 160+ sites in 28 countries, and therefore covers a broader range of geographies than the US-based Flatiron RWD; differences in background care across geographies and care settings may contribute to differences in outcomes between the CTD and RWD.

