The Flatiron Health EHR database is a longitudinal, de-identified real-world database derived from EHRs collected in US cancer clinics. The database covers more than 2.6 million active cancer patients treated at over 800 sites of care across 4 US census regions. Patient-level data includes both structured (diagnosis, demographics, laboratory values, biomarker information, drug orders, visits, etc.) and unstructured (physician notes, radiology, and pathology reports, etc.) sources. Data on death is drawn from structured or unstructured data fields in the EHR, and publicly available sources of mortality including the US Social Security Death Index, and commercial obituary data. 13

Pfizer has contracted with Flatiron for a custom data extract containing information on patients with advanced melanoma who received treatment with BRAF- or MEK-inhibitor therapies. Patients meeting the eligibility criteria defined for this study will be obtained from this custom data extract and used in all analyses.

Treatment/cohort labels

The analysis will focus on the following targeted therapy regimens:

- Encorafenib + binimetinib (ENCO+BINI), pooled across COLUMBUS and Flatiron EHR
- Dabrafenib + trametinib (DAB+TRAM), from Flatiron EHR
- Vemurafenib + cobimetinib (VEM+COBI), from Flatiron EHR

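### The metastatic-burden rows of Appendix Table 1 confound treatment with data source, because one ENCO+BINI column mixes trial-collected and ICD-derived data

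*Protocol*

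**What the plan says.** SAP 2.1 defines the first cohort as "Encorafenib + binimetinib (ENCO+BINI), pooled across COLUMBUS and Flatiron EHR"; the other two cohorts come from Flatiron alone.

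For number of organs and for each metastasis row, protocol 8.3 (Table 1) says of the trial side: "This data was collected and reported in COLUMBUS". For organ count it then says: "In Flatiron EHR, it will be derived based on counting the number of distinct sites recorded as having metastases based on ICD codes". Lung, liver and other metastases in Flatiron likewise depend on the presence of ICD codes. SAP Section 5 has the same definitions.

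Protocol 8.9 states that "metastases will very likely be underestimated in the Flatiron EHR". It adds that these data are not comparable with COLUMBUS and rules out adjusting for them. It draws no consequence for the descriptive table, and the SAP text has no equivalent caveat.

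The shell "Appendix Table 1: Baseline patient characteristics, by treatment group" (protocol appendix and SAP 9.1) nevertheless prints all four variables under a single ENCO+BINI heading beside the two comparators. It also has a row for AJCC stage at treatment initiation, which protocol 8.3 describes as "Not available in the Flatiron EHR".

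On purpose, protocol Section 6 says: "Baseline profiles of patients will also be compared to characterize differences in patients receiving different therapies". SAP Section 2 repeats this.

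**The concern.** The plan judges these variables too different between sources to be used for adjustment, then sets them side by side by treatment. Under-recording in Flatiron affects every comparator patient but only the Flatiron share of ENCO+BINI. Part of any printed gap may therefore be measurement, and the table gives no means of separating that part from a real difference.

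Metastatic burden is the example 8.9 gives of a factor left unadjusted, so this table is a natural place to judge which way residual confounding runs. If ENCO+BINI looks more heavily burdened only because the trial recorded sites more completely, a favourable adjusted hazard ratio could be taken as conservative without good reason.

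Under-recording may also be hard to see. A Flatiron patient with three sites of which one is coded appears as having one organ involved, not as missing.

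**Working it through.** The documents give no figure to reproduce here: no prevalence of metastatic sites, no ICD capture rate and no number of Flatiron ENCO+BINI patients.

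**Inputs**
- COLUMBUS ENCO+BINI patients: 192 (protocol 8.4), assuming all enter the table.
- Flatiron ENCO+BINI patients, nF: not given. The protocol's summary of changes says only that the cohort was too small for adjusted analysis. Assumed 30 to 100, with 192 as an extreme.
- True proportion with the characteristic, p: not given. Assumed 30% to 45%.
- ICD capture, s (probability that a true positive is coded): not given. Assumed 0.5 to 0.9. An uncoded site is taken as absent, with no false positives.

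**Formula.** Let w = 192/(192 + nF). With the same true p in every group:
- printed ENCO+BINI = w·p + (1 − w)·s·p
- printed comparator = s·p
- artefact = w·p·(1 − s), which is above zero whenever s < 1

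**Results with equal true burden**

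| p | s | nF | w | ENCO+BINI | Comparator | Artefact (points) |
|---|---|---|---|---|---|---|
| 45% | 0.5 | 30 | 0.865 | 42.0% | 22.5% | 19.5 |
| 45% | 0.6 | 60 | 0.762 | 40.7% | 27.0% | 13.7 |
| 45% | 0.8 | 100 | 0.658 | 41.9% | 36.0% | 5.9 |
| 30% | 0.9 | 100 | 0.658 | 29.0% | 27.0% | 2.0 |
| 30% | 0.9 | 192 | 0.500 | 28.5% | 27.0% | 1.5 |

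First row: 192/222 × 0.45 × 0.5 = 0.195. Third row: 192/292 × 0.45 × 0.2 = 0.059.

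**Unequal true burden.** Let the trial proportion be pT and the Flatiron proportion p in all three Flatiron cohorts. The printed difference is w·(pT − s·p), so its sign reverses when pT < s·p. With p = 40% and nF = 30:
- s = 0.7, pT = 0.6 × 40% = 24%: 0.865 × (0.24 − 0.28) = −0.035
- s = 0.9, pT = 0.8 × 40% = 32%: 0.865 × (0.32 − 0.36) = −0.035

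In both cases ENCO+BINI prints about 3.5 points lower than the comparator.

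**After a split by source.** With equal true burden, comparing Flatiron columns only gives s·p − s·p = 0, provided s is the same in all Flatiron cohorts.

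**The case against.** A reader might infer that the table is bound to show ENCO+BINI as sicker. The documents do not support that. Protocol 8.9 says under-recording is very likely, not certain, and what is printed is the artefact plus any true difference. COLUMBUS admitted stage IIIB and IIIC patients, whereas Flatiron patients had to start treatment after a metastatic diagnosis, so true burden may be lower in the trial. The Flatiron lung definition also takes in other respiratory organs, which pushes that row the other way. These points stand; only the direction of the measurement artefact is predictable.

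A reader might also infer that the treatment effect is biased by this table. It is not: number and sites of metastases are outside the adjustment set listed in protocol 8.7.4 and Appendix Table 3. They are candidates for the imputation models, but that is a separate question from the table layout.

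It can fairly be said that 8.9 already discloses the problem, that protocol 8.7.1 makes the listed characteristics depend on availability in both sources and on clinical input, that Section 6 names no particular table, and that only descriptive summaries are planned. The Region and Year rows would also partly reveal the mix of sources. None of this cures the defect. Both shells keep the rows, and even keep AJCC stage at initiation, which fails the 8.7.1 rule. The caveat does not sit with the table.

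The AJCC row is a lesser matter. Comparator columns that are entirely missing are visibly uninformative and do not make ENCO+BINI look sicker.

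**Conclusion.** The point holds as one of confounding between treatment and data source on the number-of-organs, lung, liver and other metastases rows. On the protocol's own expectation these rows are likely, but not certain, to overstate ENCO+BINI burden relative to the comparators. The size cannot be fixed from the documents: the 6 to 20 point range and the smaller values at 90% capture all rest on assumed prevalence, capture and Flatiron cohort size, and on equal true burden. A possible reversal does not weaken the case, because the pooled column cannot distinguish artefact from real difference in either direction.

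The harm is to the planned baseline comparison and to any reading of residual confounding drawn from it. The layout should be corrected before the table is produced; it does not call the adjusted model into question.

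**What to change.** In Appendix Table 1 of both documents:
- Show ENCO+BINI by source (COLUMBUS and Flatiron) beside the pooled column. This also shows missingness by source.
- Give no pooled ENCO+BINI figure for number of organs or for lung, liver and other metastases.
- Base any between-treatment statement on those rows on the Flatiron columns only. State that this assumes similar ICD capture across cohorts and calendar periods: eligible DAB+TRAM initiation begins in January 2014 and Flatiron ENCO+BINI in June 2018, and the definitions span ICD-9 and ICD-10. State also that the Flatiron columns do not describe the full pooled ENCO+BINI group used for the hazard ratio.
- Carry the 8.9 caveat as a footnote.
- Report AJCC stage at treatment initiation for COLUMBUS only.

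The cost is two columns and a footnote, with no new data, model or sample size. The drawback is that the Flatiron ENCO+BINI column will probably have a small N, so its percentages will be imprecise.

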Appendix Table 2: Kaplan-Meier analyses comparing OS between treatment groups

	ENCO+BINI	VEM+COBI	DAB+TRAM
	N =	N =	N =
Summary of deaths, censoring			
and median survival			
Death, n (%)			
Censored, n (%)			
Median follow-up (95% CI)			
Median OS (95% CI)			
Kaplan-Meier based estimates of % of patients remaining			
alive at different time points			
6 Months			
12 Months			
18 Months			
24 Months			
30 Months			
36 Months			

Appendix Table 3: Unadjusted and adjusted hazard ratios comparing OS between treatment groups

Results from adjusted models in Appendix Table 3 will be based on multiple imputation via multivariate imputation by chained equations. Expected adjustment factors are listed below; specific functional forms/categorization of adjustment factors will be based on the data.

	Unadjusted model	Adjusted model
	HR (95% CI)	HR (95% CI)
Treatment group		
DAB+TRAM vs. ENCO+BINI		
(ref)		

VEM+COBI vs. ENCO+BINI	
(ref)	
Adjustment factors	
Age (years)	
Male vs female	
Asian race vs. White	
Other race vs. White	
Unknown race vs. White	
BMI (kg/m²)	
ECOG (1 vs. 0)	
LDH (>ULN vs. ≤ULN)	
Treatment naïve vs. prior 1L	
IO treatment	
Prior IO/chemotherapy (Yes	
vs. No)	
Prior surgery (Yes vs. No)	
Time from initial melanoma	
diagnosis to metastatic disease	
Time from metastatic disease	
to treatment initiation
